12.2 Safety

The number and percentage of participants experiencing solicited post-vaccination reactogenicity (fever, diarrhea, vomiting, decreased appetite, irritability, decreased activity level) during the 7-day period after any dose will be tabulated by vaccine group and severity (Table 16). For the percentage within each group, an exact two-sided 95% CI will be provided using Clopper-Pearson method. The percentage of participants with at least one solicited post-vaccination reactogenicity between ROTAVIN and ROTAVIN-M1® groups after both doses and after each vaccination will be compared using a two-sided Fisher's Exact test with a significance level of 0.05. Results will be tabulated for the safety population for participants with available data. These results will be repeated after each dose (Tables 17 and 18) and are considered as supportive.

Solicited reactions will be presented by severity for each vaccine group after any vaccinations and after each vaccination (Figure 2-4).

Solicited reactions will be listed (Listing 11). Separate listings will be presented for solicited reactions ongoing on day 7 (Listing 12) and severe solicited reactions (Listing 13).

12. Secondary Analyses

13.1 Immunogenicity

For participants with a negative pre-vaccination IgA concentration (< 20 IU/ml), a participant is considered as seroconverted if the participant has a positive post-vaccination IgA concentration (≥ 20 IU/ml). For participants with a positive pre-vaccination IgA concentration, a participant is considered as seroconverted if the participant has a post-vaccination IgA concentration at least 4 times as high as the pre-vaccination IgA concentration.

Seropositivity is defined as serum IgA antibody concentration ≥ 20 IU/ml.

The number and percentage of participants with seroconversion in IgA antibodies 28 days after the second vaccination, will be summarized for each vaccine group for the PP and FA population (Tables 19 and 20, respectively). The exact 95% CI using the Clopper-Pearson method for the percentage of participants will be computed for each vaccine group. The difference in the percentage between the two groups (ROTAVIN and ROTAVIN-M1[®]) will be provided along with its two-sided 95% CI using the Miettinen and Nurminen method. The same analyses will be repeated for seropositivity for the PP and FA population (Table 21 and Table 2022 respectively).

A reverse cumulative distribution (RCD) curve for anti-rotavirus IgA concentrations will be created by vaccine group and visit for the PP and FA population (Figure 5 and 6, respectively). RCD curves are considered as supportive.

Geometric mean concentration and 95% CIs will be plotted by vaccine group for the PP and FA population (Figure 7 and 8, respectively).

13.2 Safety

13.2.1 Immediate Adverse Events

Number and percentage of participants, and total number of events, with immediate adverse events within 30 minutes after any dose and after each dose will be tabulated for each vaccine group and overall by preferred term and severity (Tables 23-25) and by preferred term and relationship with study vaccine (Table 26-27). Results will be tabulated for the safety population. For the percentage, an exact two-sided 95% CI will be provided using Clopper-Pearson method.

Immediate adverse events will be listed (Listing 14).

13.2.2 Unsolicited Adverse Events (AEs)

Solicited reactions that occur within 7 days after any study vaccination are recorded in the PIDC Reconciliation: Reactogenicity Form. Solicited reactions that become SAEs, i.e. participant was hospitalized, need to be recorded in the Serious Adverse Event Report Form. To trigger the Serious Adverse Event Report Form, the Adverse Event Form must be filled out first, which results in the solicited reactions, that become a SAE within 7 days after any study vaccination, recorded twice as a solicited reaction and an unsolicited reaction. To avoid double counting these events, they will be summarized in tables relating to solicited reactions and SAEs but not in unsolicited adverse event tables. All other reported AEs that start after vaccination and are within four weeks after each vaccination will be tabulated. If a given disease is already reported as ongoing at the first visit on the medical history pages, it will be counted and tabulated as a

vaccine emergent adverse event only if it worsens after the immunization with the study vaccine. When an adverse event occurs more than once for a participant, the maximal severity and strongest relationship to the vaccine group will be counted.

The number and percentage of participants, and total number of events, with unsolicited adverse events within four weeks will be tabulated after any dose and after each dose for each vaccine group and overall by system organ class, preferred term, and severity (Table 29-21) and by system organ class, preferred term, and relationship with study vaccine (Table 32-34). Results will be tabulated for the safety population. For the percentage, an exact two-sided 95% CI will be provided using Clopper-Pearson method.

The number and percentage of participants experiencing unsolicited AEs will be summarized after any dose and after each dose by MedDRA system organ class and preferred term (Table 35-37). This summary will be repeated for related unsolicited AEs, unsolicited AEs leading to withdrawal from the study, and unsolicited AEs leading to withdrawal from study vaccination but follow-up continued (Tables 38-42). Results will be tabulated for the safety population for each vaccine group and overall.

Unsolicited AEs by MedDRA system organ class will be presented by relationship to study vaccine (Figure 9) and severity (Figure 10) for each vaccine group.

All unsolicited AEs will be listed (Listing 15). All related unsolicited AEs will be listed (Listing 16).

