9 ASSESSMENT OF SAFETY AND ADVERSE EVENTS

9.1 Adverse Events

Adverse Event: An adverse event is defined as any untoward medical occurrence in a participant after administration of the investigational vaccine and that does not necessarily have a causal relationship with the investigational vaccine. An AE can therefore be any unfavourable and unintended sign (including abnormal laboratory findings), symptoms, physical examinations, or

disease temporally associated with the use of the investigational vaccine, whether or not related to the investigational vaccine. This definition includes exacerbations of pre-existing conditions. Stable pre-existing conditions which do not change in nature or severity during the study are not considered AEs; however, these should be reported as part of the medical history. AE's will be recorded from D1 after study vaccination up to last visit of the participant. An AE does not include:

- Medical or surgical procedures (e.g., surgery, endoscopy, transfusion), but the condition that leads to the procedure is an AE.
- Situations where an untoward medical occurrence has not occurred (e.g., hospitalization for elective surgery, social and / or convenience admissions).
- Overdose of either study drug or concomitant medication without any signs or symptoms

Information to be collected on AEs includes event description, time of onset, clinician's assessment of severity, relationship to study product, and time of resolution/stabilization of the event. AE assessment should be made only by those with the training and authority to make a diagnosis.

Solicited AEs are pre-specific adverse events that are common or known to be associated with vaccination and that are actively monitored as indicators of vaccine reactogenicity. Investigators will not be required to assess causality of solicited adverse events if the onset is during the solicitation periods. Solicited adverse events with onset after the solicitation period will be captured as unsolicited AEs.

For this trial, immediate AEs will be assessed by study staff 30 minutes after each vaccination and solicited AEs will be assessed daily for 7 days after each vaccination by the participants. Participant parent/LAR will be provided a diary to record the presence or absence of solicited AEs, severity of the solicited AE and use of concomitant medication.

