9.7 Solicited Reactions (Expected Reactions)

Specific systemic reactions will be solicited (specifically asked of participant's parent/LAR) while participants are in the study. These specific reactions, i.e. (fever, diarrhea, vomiting, decreased appetite, irritability, and decreased activity level) will be graded by the study team as per the guidance above.

Solicited Systemic Reactogenicity will be collected through study Day 7. If a solicited sign or symptom has started during the 7 days post vaccination and continues beyond the 7 days, it will continue to be reported as a reactogenicity symptom. Any solicited sign or symptom starting after 7 days post vaccination will be recorded as an "unsolicited AE".

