Unknown/lost to follow up	x (x)	x (x)	x (x)	x (x)	x (x)	x (x)
Recovered/resolved without sequelae	x (x)	x (x)	x (x)	x (x)	x (x)	x (x)
Recovered/resolved with sequelae	x (x)	x (x)	x (x)	x (x)	x (x)	x (x)
Stabilized	x (x)	x (x)	x (x)	x (x)	x (x)	x (x)
Death	x (x)	x (x)	x (x)	x (x)	x (x)	x (x)
Total Deaths – After Any Dose	x (x)	x (x)	x (x)	x (x)	x (x)	x (x)
Relationship to Study Vaccine						
Related	x (x)	x (x)	x (x)	x (x)	x (x)	x (x)
Not related	x (x)	x (x)	x (x)	x (x)	x (x)	x (x)
Total Deaths – After Dose 1	x (x)	x (x)	x (x)	x (x)	x (x)	x (x)
Relationship to Study Vaccine						
Related	x (x)	x (x)	x (x)	x (x)	x (x)	x (x)
Not related	x (x)	x (x)	x (x)	x (x)	x (x)	x (x)
Total Deaths – After Dose 2	x (x)	x (x)	x (x)	x (x)	x (x)	x (x)
Relationship to Study Vaccine						
Related	x (x)	x (x)	x (x)	x (x)	x (x)	x (x)
Not related	x (x)	x (x)	x (x)	x (x)	x (x)	x (x)

	ROTAVIN x (%)	ROTAVIN-M1 x (%)	Total x (%)
x=Number of participants with an event			
^a Percentages are based on the total number of participants in the safety population in each vaccine group and overall.			
^b Percentages are based on the total number of events reported in each vaccine group and overall.			
^c Solicited reactions that become SAEs or that start within 30 minutes of vaccination are only counted as one event for the number of events.			
^d Percentages are based on the number of participants with available data.			
Participants may experience a given event multiple times during the study with differing severities and/or outcomes relation to IP; therefore, the sum of participants may not add up to the total row for the event.			
A participant may be counted in multiple rows for a given event if they experienced the event multiple times with differing severities or relation to IP; however, they will be counted only once in the overall row for that event. Therefore, the sum of participants may not add up to the overall row for the event.			

Table 58: Vaccination Administration – Safety Population

	Dose 1			Dose 2		
	ROTAVIN N=XX x (%)	ROTAVIN-M1 N=XX x (%)	Total N=XX x (%)	ROTAVIN N=XX x (%)	ROTAVIN-M1 N=XX x (%)	Total N=XX x (%)
Was vaccination given to the participant?						
Yes	x (x)	x (x)	x (x)	x (x)	x (x)	x (x)
No	x (x)	x (x)	x (x)	x (x)	x (x)	x (x)
Reason vaccination was not given						
Receipt of licensed rotavirus vaccine from outside	x (x)	x (x)	x (x)	x (x)	x (x)	x (x)
Reaction to an earlier dose of vaccine	x (x)	x (x)	x (x)	x (x)	x (x)	x (x)

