ROTAVIN-M1	Nam Dinh	xxx	xxx	xxx	xxx	xxx	DDMMYY; hh:mm	Dose 1 (25 minutes)	DDMMYY Y; hh:mm	xxx	Severe	Yes	xxx	xxx	xxx	xxx	xxx
		xxx	xxx	xxx*	xxx	xxx	DDMMYY; hh:mm	xxx	DDMMYY Y; hh:mm	xxx	xxx	xxx	xxx	xxx	xxx	xxx	xxx
		xxx	xxx	xxx	xxx	xxx	DDMMYY; hh:mm	xxx	DDMMYY Y; hh:mm	xxx	xxx	xxx	xxx	xxx	xxx	xxx	xxx
		xxx	xxx	xxx	xxx	xxx	DDMMYY; hh:mm	xxx	DDMMYY Y; hh:mm	xxx	xxx	xxx	xxx	xxx	xxx	xxx	xxx

^aTime from vaccination is presented for immediate adverse events; otherwise days from vaccination is presented.

*Event started 4 weeks after vaccination

Severity color coding: yellow = mild, orange = moderate, red = severe, purple = life threatening, black = death

This listing includes solicited reactions that became SAEs within 7 days after any study vaccination.

Listing 16: Related Unsolicited Adverse Events – Safety Population

Treatment	Site	Participant ID	Adverse Event Code	Event Term	System Organ Class	Preferred Term	First sign or symptom date and time	Associated Dose (Days/Time post Dose) ^a	Date and Time of Resolution	Duration of Event (Days)	Severity	Immediate Adverse Event	SAE (SAE Number)	Action taken for further dose	Other action taken for treatment	Outcome
ROTAVIN	Nam Dinh	xxx	A1	xxx	xxx	xxx	DDMMYY; hh:mm	Dose 1 (12 days)	DDMMYY Y; hh:mm	3	Mild	No	No	xxx	xxx	Recovered without sequelae
		xxx	xxx	xxx	xxx	xxx	DDMMYY; hh:mm	Dose 2 (3 days)	DDMMYY Y; hh:mm	2	Moderate	No	Yes (CVIA 068-EN-001)	xxx	xxx	Recovered without sequelae
ROTAVIN-M1	Nam Dinh	xxx	xxx	xxx	xxx	xxx	DDMMYY; hh:mm	Dose 1 (25 minutes)	DDMMYY Y; hh:mm	xxx	Severe	Yes	xxx	xxx	xxx	xxx
		xxx	xxx	xxx	xxx	xxx	DDMMYY; hh:mm	xxx	DDMMYY Y; hh:mm	xxx	xxx	xxx	xxx	xxx	xxx	xxx
		xxx	xxx	xxx	xxx	xxx	DDMMYY; hh:mm	xxx	DDMMYY Y; hh:mm	xxx	xxx	xxx	xxx	xxx	xxx	xxx
		xxx	xxx	xxx	xxx	xxx	DDMMYY; hh:mm	xxx	DDMMYY Y; hh:mm	xxx	xxx	xxx	xxx	xxx	xxx	xxx

^aTime from vaccination is presented for immediate adverse events; otherwise days from vaccination is presented.

Severity color coding: yellow = mild, orange = moderate, red = severe, purple = life threatening, black = death

This listing includes solicited reactions that became SAEs within 7 days after any study vaccination.

Listing 17: Serious Adverse Events – Safety Population

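### SAP 13.2.2 times its de-duplication rule on when a solicited reaction becomes serious, not on when it began, so read literally a Day 1–7 reaction that turns serious later is tabulated as both solicited and unsolicited

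*SAP*

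**What the plan says.** **SAP 13.2.2.** When a solicited reaction becomes an SAE, the SAE form can be reached only through the AE form: "the Adverse Event Form must be filled out first". The reaction is then held both as a solicited reaction and as an unsolicited one. The SAP names the affected events as "the solicited reactions, that become a SAE within 7 days after any study vaccination" and says of them that "they will be summarized in tables relating to solicited reactions and SAEs but not in unsolicited adverse event tables". The next sentence takes up everything else: "All other reported AEs that start after vaccination and are within four weeks after each vaccination will be tabulated".

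**SAP Listings 15 and 16.** Both carry the same footnote: "This listing includes solicited reactions that became SAEs within 7 days after any study vaccination".

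**SAP Table 57, footnote c.** "Solicited reactions that become SAEs or that start within 30 minutes of vaccination are only counted as one event for the number of events".

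**Protocol 9.7.** A solicited symptom that begins in the 7 days and "continues beyond the 7 days, it will continue to be reported as a reactogenicity symptom". Protocol 9.1 sets the opposite boundary: "Solicited adverse events with onset after the solicitation period will be captured as unsolicited AEs". Protocol 9.8 repeats that onset after 7 days is what makes a solicited sign an unsolicited AE.

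**The concern.** The protocol classifies by onset date, while the SAP's exclusion is timed on seriousness. The two agree for most reactions. They part for a reaction that starts inside the solicitation window, persists, and meets a seriousness criterion (admission, for example) only after the window has closed. Such an event is solicited under the protocol and still needs an AE Form record, yet it falls outside the SAP's exclusion. The rule then produces the double count it was written to prevent.

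What is at stake is the accuracy of the unsolicited AE tables, including the hospitalisation subset. Individual rows there may hold very few infants, so one misplaced event can be noticeable. It is a matter of correct tabulation and does not touch the trial's primary conclusions.

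**Working it through.** No planned figure is in dispute, so the check is to trace cases through the rules.

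**Rules used**
- R1 (Protocol 9.1, 9.7, 9.8): onset in Days 1–7 means solicited, however long the symptom lasts; later onset means unsolicited.
- R2 (SAP 13.2.2): any solicited reaction that becomes an SAE also has an AE Form record.
- R3 (SAP 13.2.2): the AE Form record is kept out of the unsolicited tables if the reaction became an SAE within 7 days of vaccination.
- R4 (SAP 13.2.2): every other AE Form record that starts after vaccination and lies within four weeks is tabulated as unsolicited.

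| Case | Onset | Becomes SAE | R1 class | R3 met? | Solicited tables | Unsolicited tables |
|---|---|---|---|---|---|---|
| A | Day 5 | Day 6 | Solicited | Yes | Yes | No |
| B | Day 5 | Day 10 | Solicited | No | Yes | Yes, through R4 |
| C | Day 9 | Day 10 | Unsolicited | Not applicable | No | Yes |

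Only case B is counted twice. Day 10 was chosen so that the result does not depend on whether a limit of 7 days after vaccination reaches Day 7 or Day 8, given that vaccination day is Day 1.

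**Where case B lands**
- Solicited: Table 16, and Table 17 or 18 according to dose.
- Unsolicited: the set of Tables 29–37, and Table 55 if the infant was hospitalised.
- Related unsolicited, Tables 38–40: only if the AE Form records the event as related.
- SAE tables, 43–54: the same under either wording.
- Primary safety comparison (at least one solicited reaction, Fisher's exact test, SAP 12.2): the same under either wording, because the infant already counts as having a solicited reaction.

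**Size per duplicate**, using the planned group sizes of 550 and 275 (Protocol 12.2):
- Liquid arm: 1/550 = 0.0018, or 0.18 percentage points.
- ROTAVIN-M1 arm: 1/275 = 0.0036, or 0.36 percentage points.
- The percentage moves only if the infant is not already in that row for another unsolicited AE.

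**Effect on a sparse row with a planned interval** (Tables 29–34, Clopper–Pearson). The upper 95% limit for 0/n is 1 − 0.025^(1/n). For 1/n it is the p that solves (1−p)^n + n·p·(1−p)^(n−1) = 0.025.

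| n | 0 events, upper limit | 1 event, upper limit |
|---|---|---|
| 550 | 0.67% | 1.01% |
| 275 | 1.33% | 2.01% |

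**How often.** The documents give no expected number of such cases. The earlier ROTAVIN-M1 phase III trial (Protocol 2.5.3) reported three SAEs among 800 infants: encephalitis, pneumonia and bronchiolitis, all more than 40 days after vaccination. None is a solicited symptom, which points to few or no cases like B.

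**The case against.** **The intent is plain.** SAP 13.2.2 opens with reactions that occur in the 7 days, then refers without a time limit to solicited reactions that become SAEs, and says its aim is to avoid counting twice. The 7-day limit may simply have carried over from the opening sentence. That is likely, and it makes this a drafting gap and not a deliberate choice. But the clause attaches the limit to becoming an SAE, and both listing footnotes repeat it, so a programmer working from the text would filter on the date of seriousness.

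**The protocol has a similar timing rule.** Protocol 9.5 says that a solicited symptom reported as an SAE during the solicitation period goes on the diary card and the SAE form. This may be where the SAP wording came from. It governs which forms are completed, though, and does not alter the onset-based boundary in 9.1, 9.7 and 9.8. It also says nothing about a reaction that becomes serious afterwards.

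**Three stronger readings are tempting, and the documents do not support them.**
- A reader might infer that Table 57 footnote c is a second, incompatible de-duplication rule. In the shell, the superscript sits only on the row for the total number of events. It says how often an event counts in that total, whereas 13.2.2 says which category tables an event enters. It already counts case B once. That total also includes solicited reactions, so it was never meant to reconcile with the unsolicited tables alone.
- A reader might infer that case B must enter related Tables 38–40, because Protocol 9.4 treats solicited reactogenicity in the 7-day period as related. Protocol 9.1 does not require a causality assessment for solicited events, while 9.9 requires a clinician's evaluation for every SAE. The SAP nowhere says that the automatic rule overrides what is recorded on the AE Form.
- A reader might infer that counts of serious or vaccine-related serious events are inflated. They are not: the SAE and related-SAE tables hold the event once under either wording.

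**Conclusion.** The point stands as a wording error with a small effect. Read literally, SAP 13.2.2 and the Listing 15 and 16 footnotes let a solicited reaction with onset in Days 1–7 and later seriousness be tabulated both as solicited and as unsolicited, against the rule's own purpose and the protocol's onset-based classification.

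This rests on three assumptions: that the rule is programmed as worded; that the AE Form is completed for late-serious reactions too, as 13.2.2 describes; and that at least one such reaction occurs, which earlier experience suggests is unlikely. The 0.18 and 0.36 point figures use planned group sizes and are per duplicate; they do not forecast a total. No change follows for the immunogenicity analysis, the Fisher comparison of solicited reactions, the SAE tables or the total number of events in Table 57.

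**What to change.** 1. In SAP 13.2.2, define the excluded events by onset: any solicited reaction with onset in Days 1–7 after a study vaccination that becomes an SAE at any time is summarised in the solicited and SAE tables and left out of the unsolicited AE tables.
2. Reword the footnotes to Listings 15 and 16 to describe the same set of events.
3. Leave Table 57 footnote c unchanged.

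The cost is one phrase, two footnotes, and a program filter on onset date in place of the date of seriousness. No new data are needed and no primary analysis changes. It should be settled before database lock and unblinding, when Protocol 13.3 requires the SAP to be final.
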